On day 17 or 18 after the first day of taking the mouth rinse for the study, the subject will be called by a study staff member, who will review and follow up on any side-effects that the subject is experiencing and answer any questions about the study or study mouth rinse. The staff member will remind the subject to complete a subject self-assessment tool (Appendix C) and the daily log (Appendix A) (only if they are still on study mouth rinse) and bring them to the next visit. The phone call will take about 15 minutes.

5.1.8 Visit 5

This visit will occur 7 days (+/- 1 day) after Visit 4. A mucositis assessment (CTAE version 4.0 and WHO Oral Toxicity Scale) will be conducted and documented by a health provider (Appendix B), who will review and follow up on any side-effects that the subject is experiencing and obtain the daily log (Appendix A) from the subject (if the subject is still on study mouth rinse). A blood sample will be obtained to assess liver function (CMP) and clotting function (PT and INR). A blood and saliva sample will be obtained for research purposes (section 10). If the mucositis score \leq Grade 2 but is unresolved, then the subject will continue to receive the study treatment (curcumin or standard mouth rinse) until the mucositis is resolved (Grade 0). Sufficient mouth rinse will be given to the subject for the subsequent week of the study. This visit will take approximately 30 minutes.

5.1.9 Weekly phone calls to subjects receiving study mouth rinse (curcumin or standard mouth rinse)

Between each visit, each subject will be called by a study staff member, who will review and follow up on any side-effects that the subject is experiencing and answer any questions about the study or study mouth rinse. The staff member will remind the subject to complete a subject self-assessment tool (Appendix C) and the daily log (Appendix A) and bring them to the next visit. The phone call will take about 15 minutes.

5.1.10 Weekly visits for subjects receiving study mouth rinse (curcumin or standard mouth rinse)

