5.2 Study Calendar

Study Procedure	Visit 1 (Screening)	Week 1		Week 2		Week 3		Week 4- mucositis resolution		Final visit
	day -1	Visit 2: day 0	Phone call 1: day 3	Visit 3: day 7	Phone call 2: day 10	Visit 4: day 14	Phone call 3: day 17	Visit: For phase II: weekly cycle repeated until mucositis is resolved (and no AEs)	Phone calls	
activity window		At or w/in 48hr of Visit 1	+ 1 day	+/- 1 day	+ 1 day	+/- 1 day	+ 1 day	+/- 1 day	+ 1 day	+/- 1 day
Sign Informed Consent	X									
Oral exam for hygiene	X									
Pregnancy test	X ¹									
Provider mucositis assessment ²	X	X ³		X		X		X ^a		X
Provider supplies study mouth rinse		X		X		X ^a		X ^a		X
Provider supplies study journal, self-assessment		X		X		X ^a		X ^a		X
Provider collects journal and self-assessments				X		X		X ^a		X
Remind subject to complete self-assessment		X	X		X		X		X ^a	
Blood collection for liver function (CMP) ⁴	X			X		X		X ^a		X
Blood collection for clotting (PT and INR) ⁴	X			X		X		X ^a		X
Research blood collection ⁵		X		X		X		X ^a		
Research saliva collection ⁵		X		X		X		X ^a		
Collect AEs			X	X	X	X	X	X ^a	X ^a	X
Review of concomitant medications	X	X		X		X		X ^a		X

¹ Blood or urine pregnancy test, if not already done as part of standard of care

² Includes CTAE version 4.0 and WHO oral Toxicity scale.

³ Mucositis assessment at Visit 2, only if a different day than Visit 1 (does not need to be repeated if Visit 1 and 2 are done on the same day)

⁴ Does not need to be repeated if already done for standard of care.

⁵ 6 ml of peripheral blood into a non-anti-coagulated tube, 2 ml saliva into a sterile tube; processed and stored as described in the operations manual.

^a Only if subject is still taking study mouth rinse based on improvement of mucositis at each visit, beginning at visit 4.

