5.6 Determination of MTD

The MTD will be determined as follows: If a DLT occurs in any one of the 3 patients at a specific dose level, an additional 3 patients must be treated at that dose level to achieve statistical validity of the MTD. If 2 of the 6 patients (17%) at a dose level develop a DLT, the previous dose level will be used as the MTD. If no DLT is observed, then the MTD will be the highest dose. To ensure safety of subjects at each dose level, all assessments will be completed at Visit 5 for subjects at a dose level before another subject is given study drug at the

subsequent dose level.

6. Expected Adverse Events

Toxicities will be graded by health care providers using the Common Terminology Criteria for Adverse Events (CTCAE) Version 4.0 weekly after initiation of study mouth rinse until mucositis is resolved (Grade 0) (see Provider Assessment in calendar, section 5.2). Toxicities will be assessed by subject self-evaluation during study mouth rinse administration between clinic visits (see Subject Assessment in calendar, section 5.2).

Very few studies have reported any severe or serious side effects from curcumin and most studies have involved oral administration of curcumin. No major toxicity has been found in studies where curcumin is used short-term. Increased bleeding may occur due to inhibition of platelet aggregation (very rare). Possible other side effects associated with curcumin include: vomiting, nausea, rash and GI distress. In a study of subjects with colon cancer, oral curcumin at doses ranging from 0.45 to 3.6 gram/day for 1 to 4 months was associated with nausea and diarrhea and caused an increase in serum alkaline phosphatase and lactate dehydrogenase[15]. In one study of patients with advanced pancreatic cancer, 5 of the 17 patients receiving oral curcumin (8 gram/day) in combination with gemcitabine reported intractable abdominal pain after a few days to 2 weeks of curcumin intake[16]. In a recent study of topical curcumin for mucositis in juveniles and children[14], there were no oral adverse events documented and no systemic adverse events that possibly could be related to the use of the curcumin mouthwash.

Patients will receive full supportive care as appropriate. The rationale for treatment, dosage and the date of treatment will be recorded in the medical record.

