6.2 Criteria for Subject Removal

A subject will be removed from the study for the following reasons:

- Dose limiting toxicity.
- No improvement in mucositis after 14 days of taking the study mouth rinse.
- Patient decision to withdraw consent or discontinue the study.
- Deemed by the physician to be the best medical interest of the patient.
- At the discretion of the investigator, patients who are non-compliant.

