This study will involve 12 subjects in the first part, plus an additional 3 subjects if a dose-limiting toxicity occurs (see section 2). This sample size is similar to other phase I dose escalation studies and will result in a determination of maximum-tolerated dose. The first objective for the second part (n=46) is to determine whether curcumin decreases an objective measurement of oral mucositis. Mucositis assessment will be conducted by the provider using the WHO scale and CTCAE scale. The scales are continuous between 0 and 4. Analysis of variance will be used to compare the two groups of subjects (standard mouth rinse versus study mouth rinse) separately for each time period (baseline and each week after study mouth rinse initiation). In a one-way ANOVA study, sample sizes of 23, and 23 are obtained from the 2 groups whose means are to be compared. The total sample of 46 subjects achieves 91% power to detect differences among the means versus the alternative of equal means using an F test with a 0.05 significance level. The size of the variation in the means is represented by their standard deviation which is 0.50. The common standard deviation within a group is assumed to be 1.00.

9. Measurement of Effect

Differences between the two mouth rinse groups will be studied with the chi-square test for categorical factors and the analysis of variance F-test for continuous variables with a 0.05 significance level.

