9.4 Determination of the duration of mucositis

The healing time will be calculated using the health provider's assessment of mucositis (CTCAE and WHO scales) by determining the number of days between study mouth rinse initiation and the day on which grade 0 is achieved.

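### Subjects with no improvement at day 14 leave the study, so the slowest healers may have no healing time and the duration comparison can be biased in either direction

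*Combined protocol and SAP*

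**What the plan says.** Duration of mucositis is one of four secondary objectives (Section 2). Section 9.4 measures it as "the number of days between study mouth rinse initiation and the day on which grade 0 is achieved". Section 9 assigns the chi-square test to categorical factors and "the analysis of variance F-test for continuous variables with a 0.05 significance level". Section 8 plans the mucositis score comparison "separately for each time period (baseline and each week after study mouth rinse initiation".

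Section 6.2 lists the reasons for removal from the study, not only from the rinse. One of them is "No improvement in mucositis after 14 days of taking the study mouth rinse". The visits after Visit 5 are headed "Weekly visits for subjects receiving study mouth rinse (curcumin or standard mouth rinse" (Section 5.1.10). In the Section 5.2 calendar, the provider mucositis assessment in the weekly column carries footnote a: "Only if subject is still taking study mouth rinse based on improvement of mucositis at each visit, beginning at visit 4".

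Some text points the other way:
- The weekly column is headed "weekly cycle repeated until mucositis is resolved (and no AEs".
- Section 6 asks for toxicity grading "weekly after initiation of study mouth rinse until mucositis is resolved (Grade 0", but refers to the same calendar. Section 9.5 limits grading to the period of rinse use.
- Section 5.1.8 (Visit 5, about day 21) describes a provider assessment and limits only the daily log to subjects on rinse.
- The calendar's Final visit has an assessment without footnote a.

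No section gives a censoring rule, a time-to-event method, an imputed value or off-rinse follow-up for a subject in whom Grade 0 is not observed.

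**The concern.** Read together, these rules make the existence of a healing time depend on the subject's own day-14 result, which is a post-randomization outcome that treatment may affect. The subjects who lose their value are those healing most slowly, and they carry most of the information about duration. Section 1 says symptoms improve slowly over a few weeks after the peak, so the protocol itself expects some healing after day 14.

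Randomization no longer protects a comparison restricted in this way. If curcumin reduces non-improvement, the restriction hides benefit. If the arms lose different shares of slow healers for other reasons, it can create a difference where none exists. Weekly score comparisons after day 14 have a related problem: non-improvers drop out of them, and so do healed subjects, who are off rinse.

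**Working it through.** **The plan's own figure.** Section 8: 23 + 23 subjects, SD of the means 0.50, within-group SD 1.00, alpha 0.05. Noncentrality = 46 × (0.50/1.00)² = 11.5 on 1 and 44 degrees of freedom, giving power 0.912. The stated 91% reproduces. It concerns the mucositis grade; no power is stated for duration.

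**Tracing a part-2 subject with no improvement at Visit 4.**
1. Section 6.2: removed from the study.
2. Section 5.1.8: Visit 5 might still take place, since its assessment is not limited to subjects on rinse. But the subject has been removed, and the calendar has no column named Visit 5: day 21 falls in or near the weekly column with footnote a.
3. Section 5.1.10 and footnote a: no weekly assessment afterwards.
4. Final visit: undated, and not stated to cover removed subjects.
5. Section 9.4: no observed Grade 0, so no healing time.
6. Section 9.6: 14 days × 3 doses = 42, and 0.70 × 42 = 29.4, so 30 doses make this subject evaluable for efficacy. The evaluability rule does not resolve the missing value.

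A subject who improves but stays above grade 2 (say 4 to 3) is not removed, yet Sections 3 and 5.1.6 give no instruction to continue rinse, and no weekly visit is described after Visit 5.

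**Illustration 1 (all inputs assumed).** Let mean healing be H_o days in subjects not removed and H_n in non-improvers, equal across arms, with non-improver shares p_c (control) and p_e (curcumin).
- True difference = (p_c − p_e)(H_n − H_o).
- Difference among subjects not removed = H_o − H_o = 0.

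| p_c − p_e | 7 extra days | 14 extra days | 21 extra days |
|---|---|---|---|
| 0.10 | 0.7 | 1.4 | 2.1 |
| 0.20 | 1.4 | 2.8 | 4.2 |
| 0.30 | 2.1 | 4.2 | 6.3 |

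Entries are true differences in days, all shown as 0 by the restricted comparison.

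Now let Visit 5 catch a removed subject who heals at day 21. Take p_c = 0.40 and p_e = 0.20. Improvers heal at days 7/14/21 with probability 0.25/0.5/0.25 (mean 14). Non-improvers heal at days 21/28/35 equally (mean 28).
- Control: (0.60 × 14 + 0.133 × 21)/(0.60 + 0.133) = 15.27 days.
- Curcumin: (0.80 × 14 + 0.067 × 21)/(0.80 + 0.067) = 14.54 days.
- Difference 0.7 days, against a true 0.20 × 14 = 2.8 days.

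Simulation of the same scenario without the Visit 5 look (4,000 trials, 23 per arm): about 14 versus 18 subjects have a value, the mean difference is about 0.05 days, and ANOVA is significant in about 5% of trials. With everyone followed to Grade 0, the difference is about 2.8 days, and log-rank and ANOVA are each significant in about 22%. With equal shares of 0.20 and no other effect, all rejection rates are about 5%.

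**Illustration 2 (different assumed model).** Exponential healing read at weekly visits, with a share of those unhealed at day 14 removed and left out.
- Means 21 (control) and 14 (curcumin) days: the difference is about 6.8 days with full data, 5.1 days if half of the unhealed are removed in both arms, and 0.3 days if all are. F-test rejection falls from 24% to 15% to 5%.
- Equal means of 21 days, with 60% of the unhealed removed in one arm and 20% in the other: a spurious difference of about 4.5 days and a false-positive rate of about 10%. Its sign depends on which arm loses more.

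**The case against.** **The dropped subjects are inferred.** A reader might infer that the plan specifies ANOVA on healed subjects only. It does not: no test is named for duration, and nothing says unhealed subjects are excluded. This stands. The supported statement is that Sections 9 and 9.4 lead there by default, because no other rule is given. The analysis could be settled later; the missing observations could not be recovered.

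**Follow-up may not stop at day 14.** A reader might infer that non-improvers are never seen again. Section 5.1.8 leaves a day-21 look arguable. Section 11 lists duration, and mucositis grade over the whole course of the study, as data to collect without an on-rinse limit. This softens the point, but neither text overrides removal from the study, and one look does not capture later healing.

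**A numerical bound looks available, but is not.** Section 6.3 stops the study if fewer than 5 of the first 10 curcumin subjects are at Grade 0 at Visit 4. A reader might infer that up to 5 + 13 = 18 of 23 curcumin subjects lose their healing time. That counts unresolved subjects. Those who improved to grade 2 or less stay on rinse and are followed weekly to Grade 0. Non-improvers are an unstated part of the unresolved and may be few: Section 1 puts onset at day 4 to 5 and the peak near day 10, so Visit 4 (4 + 14 = day 18 or later, within one cycle) falls after the peak. This stands in full.

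**The stakes are limited.** The primary objective is the MTD, and duration has no power statement. Even with full follow-up, the first scenario gives only about 22% power. This limits the consequence, but the objective is a named one, and a biased estimate is worse than an imprecise one.

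**Conclusion.** The gap is real and should be fixed. Sections 6.2, 5.1.10, 9 and 9.4 and footnote a, followed as written, leave day-14 non-improvers without follow-up to healing and without a rule for their missing healing time. On the natural reading, the duration comparison then selects on a post-randomization outcome.

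The size is not derivable from the documents. The figures above rest on assumed non-improver shares and healing times. In the 2.8-day scenario the plan would show 0 to 0.7 days, depending on whether Visit 5 is held. The bias is zero if both arms have the same share of non-improvers and curcumin shortens healing equally in everyone.

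A reader might infer that the rule favours one arm. The documents do not support that: it can hide a benefit, hide a harm or create a difference. Nor does it undermine the trial's other results. The MTD, comparisons through day 14, the 91% power and the Visit 4 futility rule do not depend on follow-up after day 14 in part 2.

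**What to change.** (a) **Section 6.2.** Let non-improvement, and likewise DLT or non-compliance, stop the rinse without ending follow-up, unless consent is withdrawn. State in Sections 3 and 5.1.6 that continuing rinse at grade 2 or less requires improvement. This also settles the case of a subject unchanged at grade 2, who is now both told to continue and due for removal.

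(b) **Sections 5.1.10 and 5.2.** Remove footnote a from the provider mucositis assessment row. Assess all randomized part-2 subjects, on or off rinse, weekly to Grade 0 or to a common fixed day in both arms, for example day 42. Record other mucositis treatment after rinse stops, and say in Section 5 that the ban on other topical treatment ends then.

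(c) **Sections 9, 9.4 and 9.6.** Analyse duration as time to Grade 0 (Kaplan-Meier, log-rank) in all randomized subjects, censoring those without Grade 0 at their last assessment or the common end day. Section 9.6 must change too, because its 70% dose rule now defines the efficacy set.

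(d) **Weekly scores after day 14.** Follow-up that ends at Grade 0 does not repair these. Carry healed subjects forward as Grade 0, or limit the comparison to day 14.

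The follow-up matters more than the choice of test: in the first simulation, ANOVA and log-rank performed alike once everyone was observed. Censoring matters for those still unhealed at the end.

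**Cost.** Wording changes, one calendar row and, since Visit 5 already covers day 21, at most about three short assessments per off-rinse subject (days 28, 35 and 42). Later healing in non-improvers may partly reflect other care, which is why that care should be recorded.

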6.3 Criteria for Study Discontinuation

If 2 patients develop a DLT at dose 1, then the trial will be closed due to unacceptable toxicity. If any patient has Grade V toxicity, then, the trial will be placed on immediate hold until the protocol investigators, the sponsor of the IND, the IRB and the FDA have been notified and a determination has been made as to the re-opening of this trial.

If < 5 of the first 10 subjects in the curcumin arm of the second part of the study have Grade 0 mucositis (CTAE version 4.0 and WHO Oral Toxicity Scale) at Visit 4, then the study will be discontinued due to lack of activity.

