The second part of the study is an expansion at the MTD. Subjects will be randomized 1:1 to an experimental arm (curcumin) and a control arm (standard of care), with 23 subjects enrolled to each arm. Subjects on the experimental arm will use a mouth rinse containing the MTD of curcumin 3 times each day for 14 days. Subjects on the control arm will use a standard mouth rinse 3 times each day for 14 days. Both mouth rinses will be used for 30 seconds and then swallowed. Subjects will be evaluated for response and toxicity. Statistical analysis of the response data will determine whether oral exposure to curcumin reduces mucositis.

Section	Contents	Page
1	1. BACKGROUND AND SIGNIFICANCE	4
2	OBJECTIVES / ENDPOINTS	5
3	STUDY DESIGN	5
4	SUBJECT SELECTION	6
4.1	INCLUSION CRITERIA	6
4.2	EXCLUSION CRITERIA	6
5	STUDY PROCEDURES AND SCHEDULE	6
5.1	STUDY VISITS	7
5.2	STUDY CALENDAR	10
5.3	PREPARATION OF STANDARD MOUTH RINSE	11
5.4	PREPARATION OF STUDY MOUTH RINSE (CURCUMIN)	11
5.5	STUDY DRUG (CURCUMIN) DOSE	11
5.6	DETERMINATION OF MTD	11
6	EXPECTED ADVERSE EVENTS	12
6.1	DOSE-LIMITING TOXICITY	12
6.2	CRITERIA FOR SUBJECT REMOVAL	12
6.3	CRITERIA FOR STUDY DISCONTINUATION	13
6.4	CRITERIA FOR DOSE REDUCTION	13
6.5	SERIOUS ADVERSE EVENTS (SAEs)	13
7	BENEFITS	13
8	SAMPLE SIZE	13
9	MEASUREMENT OF EFFECT	14
9.1	DETERMINATION OF OBJECTIVE MEASUREMENT OF ORAL MUCOSITIS	14
9.2	DETERMINATION OF SUBJECTIVE MEASUREMENT OF ORAL MUCOSITIS	14
9.3	DETERMINATION OF PAIN ASSOCIATED WITH ORAL MUCOSITIS	14
9.4	DETERMINATION OF DURATION OF MUCOSITIS	15
9.5	DETERMINATION OF TOXICITY PROFILE	15
9.6	CRITERIA TO BE EVALUABLE FOR EFFICACY AND SAFETY	15
10	CORRELATIVE STUDIES (LABORATORY STUDIES)	15
10.1	SAMPLE COLLECTION	15
10.2	EVALUATION OF PROINFLAMMATORY CYTOKINES	15
10.3	FUTURE RESEARCH AND SAMPLE DISPOSITION	16
11	DATA COLLECTION	16
12	MONITORING PLAN	16
13	REPORTING REQUIREMENTS	17
13.1	REPORTING REQUIREMENT FOR SERIOUS ADVERSE EVENTS (SAEs)	18
14	REGULATORY REQUIREMENTS	18
14.1	INFORMED CONSENT	18
14.2	INSTITUTIONAL REVIEW BOARD	19
14.3	SUBJECT CONFIDENTIALITY	19
15	EXPERIENCE OF THE INVESTIGATORS	20
16	REFERENCES	21

APPENDICES: A: DAILY LOG
B: HEALTH CARE PROVIDER ASSESSMENT TOOL
C: SUBJECT ASSESSMENT TOOL
D: BIOSKETCH FOR DR. [name]

1. Background and Significance

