6.1 Dose-limiting Toxicity

DLT resulting from any treatment component of the study will be defined in the list below. There will be no dose reductions in response to DLT.

- Any grade 2 or greater allergic response
- Any grade 3 or greater toxicity

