6.4 Criteria for Dose Reduction

Subjects taking the curcumin-containing mouth rinse that experience intolerable or prolonged (>14 days) grade 2 toxicity will receive the next lowest dose from the dose escalation part of the study.

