Careful evaluation to ascertain the toxicity and efficacy of topical curcumin on mucositis will be performed by the Principal Investigator and the research team. For all patients, the Principal Investigator will review all serious adverse events and will monitor the data and toxicities to identify trends weekly during the study. The Principal Investigator will be responsible for revising the protocol as needed to maintain safety. The IRB will review submitted adverse events to also evaluate trends and will require a follow up plan from the Principal Investigator whenever a trend is identified. Independent quality, compliance and safety monitoring of the study will occur at least once each year that the study is enrolling subjects and may include a review of protocol compliance, informed

consent documentation, data collection accuracy, adverse event reporting, patient safety and outcomes analysis.

13. Reporting Requirements

- Subject data accrued on this study will be reported in accordance with 21CFR 312.32.
- This study will utilize the CTCAE Version 4.0 for Adverse Event (AE) Reporting. The CTCAE v4.0 can be downloaded from the CTEP home page (<http://ctep.info.nih.gov>).
- The Principal Investigator will notify the IRB, and the FDA and other regulatory agencies of all serious adverse events as required by law or regulation.
- Reporting requirements to the Aurora IRB is described in IRB SOP RR:403 Ongoing Oversight of Approved Research and Reporting of Problems/Events.
- Reporting requirements to the FDA is described in the “Guidance for Industry and Investigators Safety Reporting Requirements for INDs and BA/BE Studies” December 2012:
<http://www.fda.gov/downloads/Drugs/GuidanceComplianceRegulatoryInformation/Guidances/UCM227351.pdf>.
- All participating investigators will be notified of IND Safety Reports by email.

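### Part 2 has a numerical stopping rule for lack of activity but none for toxicity: with an MTD above dose 1, no number of non-fatal DLTs among the 23 curcumin subjects pauses randomisation

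*Combined protocol and SAP*

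**What the plan says.** Part 1 treats 3 subjects per level at four levels (1, 3, 6 and 9 g/day), with 3 more if one of the first 3 has a DLT. Section 5.6 then sets the limit: "If 2 of the 6 patients (17%) at a dose level develop a DLT, the previous dose level will be used as the MTD". Where every level is free of DLTs, the highest dose becomes the MTD. Section 6.1 defines a DLT as a grade 2 or greater allergic response or "Any grade 3 or greater toxicity".

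Part 2 is described in the Precis: "Subjects will be randomized 1:1 to an experimental arm (curcumin) and a control arm (standard of care), with 23 subjects enrolled to each arm". The curcumin arm receives the MTD.

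Section 6.3 holds three triggers:
- a DLT count at the lowest dose: "If 2 patients develop a DLT at dose 1, then the trial will be closed due to unacceptable toxicity";
- an immediate hold for any Grade V toxicity;
- discontinuation for lack of activity if fewer than 5 of the first 10 Part 2 curcumin subjects are at Grade 0 at Visit 4.

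Other safety provisions:
- Section 6.2 opens "A subject will be removed from the study for the following reasons" and lists a DLT first.
- Under section 6.4, subjects with intolerable or prolonged grade 2 toxicity on curcumin "will receive the next lowest dose from the dose escalation part of the study".
- Section 12 has the Principal Investigator look for trends weekly and adds "The Principal Investigator will be responsible for revising the protocol as needed to maintain safety". The IRB also reviews adverse events and "will require a follow up plan from the Principal Investigator whenever a trend is identified". Independent monitoring takes place at least yearly.
- Section 13 requires immediate reporting of SAEs to the Principal Investigator, and reporting to the IRB and FDA as regulations require.

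**The concern.** Most curcumin exposure at the MTD happens in Part 2, and the dose is chosen from very few subjects. A dose that section 5.6 would reject if its rate were known can pass by chance. Part 2 is where that error would show, yet the section gives a number for too little healing and none for too much toxicity.

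Section 6.2 protects the subject who has had the DLT. The next subject is protected by section 12, but only once someone judges that a trend exists. A count fixed in advance makes that trigger independent of who is looking. What is at stake is the safety of later Part 2 subjects. No endpoint or test is affected.

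**Working it through.** **Inputs.** From the documents: 3 subjects per level, expanding to 6 (sections 3 and 5.6); limit of 2 of 6 (5.6); 23 curcumin subjects (Precis and section 3). The documents give no target or expected DLT rate, so every true rate p below is an assumption, shown over a range.

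**1. The plan's own figure.** Section 5.6 prints 17% beside 2 of 6. But 2/6 = 33%, and 1/6 = 17%. The percentage does not match the count. The count is what operates the rule, so I take the limit as 2 of 6, or 33%.

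**2. Which triggers can act in Part 2 above dose 1.** The DLT count names dose 1. The activity rule counts healing. The Grade V hold needs a fatal event. The 2-of-6 rule only selects the MTD. No rule counts non-fatal DLTs.

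**3. Chance that a level passes its Part 1 step, if tested.** A level passes with 0 of 3, or with 1 of 3 followed by 0 of 3. I take 2 or more of the first 3 as a failure.

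s(p) = (1−p)³ + 3p(1−p)² × (1−p)³

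- p = 25%: 0.422 + 0.178 = 0.600
- p = 33%: 0.296 + 0.132 = 0.428
- p = 50%: 0.125 + 0.047 = 0.172

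**4. Chance that a 33% level becomes the MTD.** This is lower, because every lower level must also pass and the next level must fail or not exist. With s(5%) = 0.973, s(10%) = 0.906 and s(20%) = 0.709:

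- rates 10/20/33/50%: 0.906 × 0.709 × 0.428 × (1 − 0.172) = 0.228
- rates 5/10/20/33% (top level): 0.973 × 0.906 × 0.709 × 0.428 = 0.268
- rates 10/33/50/60%: 0.906 × 0.428 × (1 − 0.172) = 0.321

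**5. Consequence if it does.** Expected DLTs among 23 = 23 × 1/3 = 7.7, with no count that pauses randomisation.

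**6. A rule in line with 2 of 6.** Take the smallest count that is at least one third: 10/3 = 3.3 gives 4; 15/3 = 5 gives 5; 20/3 = 6.7 gives 7. With Xₙ the DLT count in the first n curcumin subjects,

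P(pause) = P(X₁₀ ≥ 4) + P(X₁₀ ≤ 3, X₁₅ ≥ 5) + P(X₁₀ ≤ 3, X₁₅ ≤ 4, X₂₀ ≥ 7).

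At p = 33% this is 0.441 + 0.185 + 0.041 = 0.667. Pausing as soon as the count is reached gives the same probabilities, because a count never falls. It only brings the pause forward.

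| Assumed true DLT rate | P(pause) |
|---|---|
| 10% | 2% |
| 17% | 12% |
| 20% | 20% |
| 25% | 37% |
| 33% | 67% |
| 50% | 97% |

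**The case against.** The strongest case against is that Part 2 is already watched. Part 2 is planned over 18 months including follow-up, so 23 curcumin subjects arrive at about 23/18 = 1.3 per month, and weekly review falls about three times between one subject and the next. DLTs that are also SAEs reach the IRB and FDA under section 13. Section 6 reports no major toxicity with short-term curcumin. This stands as a reason to call the change an improvement and not a serious defect. It does not supply a threshold: action still waits on a judgement, and a non-serious grade 3 DLT would not go through SAE reporting. Section 6 also reports intractable abdominal pain in 5 of 17 patients (29%) on 8 g/day with gemcitabine. No grade is given, so this is not a DLT rate, but a substantial rate near the top dose cannot be dismissed.

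The proposed rule is also modest. At a true 33% it does not pause one time in three, and restart remains a judgement. That is accepted: it is a prompt for review, and a tighter limit costs more false alarms. A 17% limit (2 of 10, 3 of 15, 4 of 20) would pause 31% of the time at a true rate of 10%.

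A reader might infer two stronger things. One is that Part 2 has no safety oversight. The provisions listed above contradict that. The other is that the dose-1 rule, which names no Part, would close the trial after 2 DLTs among 23 subjects if dose 1 were the MTD, or through subjects reduced from dose 2 to dose 1 under section 6.4. The documents do not support that as the intended meaning. Section 5.6 falls back on the previous level, dose 1 has none, and the closure rule fills exactly that hole. Where section 6.3 means Part 2, it says so. This is a matter of wording only.

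**Conclusion.** The point holds for Part 2 with an MTD above dose 1: section 6.3 has no DLT count or rate that pauses randomisation short of a death. On the natural Part 1 reading of the dose-1 rule, the same is true if dose 1 is the MTD.

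The size depends on a DLT rate that the documents do not give. At an assumed 33%, the level becomes the MTD with probability 23% to 32% in the three scenarios shown, and 7.7 DLTs would then be expected among 23. The existing safeguards make a run of unnoticed DLTs unlikely, but none fixes when to stop and look. This is an inexpensive safety improvement. The dose-1 wording is a minor clarification.

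**What to change.** Add to section 6.3: Part 2 randomisation pauses for safety review, without automatic closure, as soon as curcumin-arm DLTs as defined in 6.1, counted at the assigned dose, reach 4 within the first 10 subjects, 5 within the first 15 or 7 within the first 20. Before restart, the review compares all events meeting 6.1, including grade 2 or greater allergic responses, with the concurrent control arm. The text should name who decides on restart. State one limit, the 2-of-6 (33%) limit of section 5.6, and correct the printed 17% to match.

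In the same section, state that the dose-1 closure applies to the Part 1 dose-1 cohort (2 of up to 6).

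The cost is protocol wording, using toxicity data that the Principal Investigator already reviews weekly. The downside is an occasional unnecessary pause: 2% at a true rate of 10% and 12% at 17%. It rises if background chemotherapy toxicity is counted, for example to 20% if the total counted rate is 20%. That is why the trigger should be a review against the control arm and not closure.
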